## 1. BACKGROUND AND SIGNIFICANCE

Post-operative delirium (POD), commonly encountered after surgery, is an acute brain dysfunction characterized by disturbances in attention, awareness, and cognition not explained by a preexisting neurocognitive disorder. Although the increased mortality rates ascribed to delirium remain debatable, delirium remains a leading cause of preventable morbidity in hospitalized elderly patients. It is also associated with prolonged hospitalization, prolonged institutionalization, and long-term cognitive deficits. The total healthcare cost attributable to delirium is estimated between \$143 and \$152 billion annually. Thus, principled strategies to pre-emptively identify and target patients at risk for delirium may result in significantly improved peri-operative outcomes.

Sleep is a naturally occurring state of decreased arousal that is crucial for normal immune and cognitive function. Basic science and clinical studies suggest sleep disturbance as a modifiable risk factor for post-operative delirium (POD). Sleep deprivation, which is associated with increased pro-inflammatory cytokine levels including interleukin-6, precedes the onset of delirium in some patients. A recent investigation linking brain activity of microglia, astrocytes, interleukin-6 and delirium in humans, suggests a mechanistic link between sleep deprivation, brain inflammation and delirium. Further, conditions associated with delirium are characterized by activation of the inflammatory cascade with acute release of inflammatory mediators. Increasing age is a significant risk factor for the development of delirium. Notably, aging is associated with activated brain glia cells. Following a systemic challenge such as critical illness, these activated glia have been suggested to facilitate an exaggerated neuroinflammatory state that predisposes to delirium. Thus, as systemic inflammation may be involved in the pathophysiology of delirium, sleep disturbance may constitute a modifiable risk factor for POD. However, structured studies are necessary to make clear the extent to which this association exists and is modifiable.

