## AIM 1: To use PSG and a validated sleep questionnaire to characterize sleep quality in POD patients Hypothesis 1.1. POD will be associated with significantly decreased pre-operative total sleep time

Hypothesis 1.2. POD will be associated with a pre-existing history of sleep disruption as measured by the Pittsburgh Sleep Quality Assessment (PSQI)

AIM 2: To use serum profiling to understand the association between POD and circadian disruption Hypothesis 2.1. POD will be associated with decreased am mRNA transcript levels of clock genes (Bmal1, Clock, Per1 and Per2).

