### 4. Subject Enrollment

**Recruitment:** This study will be performed at the Massachusetts General Hospital in Boston, MA. We will enroll 100 male and female patients into the study. Cardiac surgical patients and orthopedic trauma patients represent the primary surgical patients that are admitted to the hospital prior to their surgical procedures. Thus, we will screen cardiac and orthopedic surgical schedules to identify potential eligible subjects. We will engage members of the patient's clinical care team to ask the patient if he/she is willing to have a study team member approach him/her to discuss a research study. This initial care patient contact will be performed by cardiac or orthopedic clinical staff (M.D., P.A, N.P, R.N), cardiac or orthopedic anesthesia care providers (M.D., C.R.N.A, S.R.N.A), or hospital geriatric clinicians (M.D., P.A, or N.P). Study team members will only approach patients that are interested in learning more about the study. They will explain the details of the study and provide a flyer summarizing study procedures to the patient. Formal written consent will be obtained prior to any study related procedures.

**Retention**: All subjects who provide written consent but later decline participation in the study will not be subject to any study-related follow-up.

**Remuneration:** There will be no monetary remuneration for this study.

**Procedure for informed consent:** Members of the patient's clinical care team will briefly introduce the study to the patient. Study team members will only approach patients that are interested in learning more about the study. Study team members will explain the details of study and provide a flyer summarizing study procedures to the patient. If the study team member is a non-physician (i.e. clinical research coordinator), he/she will explicitly offer the patient an opportunity to speak to physician investigators. The study team member will review and discuss the details of the research study with the patient using the informed consent document as a guide. The discussion will include all the required elements of informed consent. A formal written consent will be obtained only after all questions and concerns have been addressed.

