#### Treatment Assignment and Randomization: Not applicable.

#### 5. Study Design

Pre-operative Visit: We will obtain a written consent prior to conducting the Long-CAM, PSQI, Patient Health Questionnaire (PHQ-9), Trust in Physician Scale (TPS) and the abbreviated Montreal cognitive assessment. Next, we will place a portable PSG device at approximately 7 pm to record neurophysiological data using the Compumedics Portable PSG monitoring device. Due to clinical care concerns, patient acuity, patient unavailability and several other unforeseen factors, PSG may not be placed on all study subjects. A minimum of the following electrodes will be placed for sleep staging: Two central channels (C3 and C4), two electrooculogram channels to capture lateral eye movements, and two reference channels over the left and right mastoids.

Post-operative Day 0: PSG electrodes will be removed at approximately 6am. Additionally, we will obtain approximately 13ml of blood to be processed into mRNA to understand the association between peri-operative circadian cycle disruption of four circadian clock genes (Bmal1, Clock, Per1 and Per2) and POD. The PI will ensure that appropriate privacy and de-identification procedures are in place for the collection and storage of blood. All MGH ORs are equipped with a four-channel frontal EEG device (Sedline, Masimo, Irvine, CA). Thus, we will collect intraoperative routine EEG data that is recorded as part of routine anesthetic management. Due to clinical care concerns, patient acuity, Sedline electrode unavailability and several other unforeseen factors, blood and Sedline EEG data may not be obtained on all study subjects.

Post-operative Days 1-3: On post-operative day 1, we will obtain approximately 13ml of blood as a post-surgical measure of mRNA levels to understand the association between peri-operative circadian cycle disruption of four

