## 6. DATA ANALYSIS PLAN

Hypothesis tests will be performed using a two-sided significance level (type I error) of  $\alpha$ =0.05. Aim 1 (Hypotheses 1 and 2) outcome will be evaluated using binominal regression models with adaptive elastic net penalty to examine the association between total sleep time and POD. Patient characteristics of interest (i.e. age, gender, baseline cognitive score, pain, depression symptom score, frailty index, Charlson comorbidity index) will be included into this regression model. Because missing data rarely occur entirely at random, we will assess associations between patient characteristics with respect to missing data. If patients with at least one missing outcome value are different from those with complete outcomes data, we will use multiple imputation to assign values to missing data risk factors and outcomes in regression modeling. Aim 2 (Hypothesis 1) Wilcoxon rank-sum tests with corrections for multiple comparisons will be used to assess differences for each analyte or transcript. In other exploratory analysis, we will assess differences in the EEG (PSG and intraoperative) dynamics of delirious and non-delirious patients. To assess statistical significance for the difference in EEG spectra at each frequency, we will compute the 99% confidence interval of the median difference between groups by using an empirical bootstrap approach. The null hypothesis will be rejected only if the confidence interval of the median difference at each frequency exceeds the significance threshold over a contiguous frequency range  $\geq$  2W. We will also characterize differences in sleep microstructure dynamics (i.e. spindle power, spindle rate, spindle peak frequencies, slow-delta phase- spindle amplitude modulation) between groups using algorithms developed in-house.

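### Aim 2's rank-sum tests are valid for a crude association; one adjusted model per transcript would cheaply show whether a difference is independent of age and surgical service

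*Combined protocol and SAP*

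**What the plan says.** Hypothesis 2.1 (Section 2) reads "POD will be associated with decreased am mRNA transcript levels of clock genes" and names four genes. Section 6 gives one confirmatory method for it: "Wilcoxon rank-sum tests with corrections for multiple comparisons will be used to assess differences for each analyte or transcript". It describes no regression, stratification, matching or sensitivity analysis for the transcripts.

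The covariates in Section 6 (age, gender, baseline cognition, pain, depression score and others) end with "frailty index, Charlson comorbidity index) will be included into this regression model". That model is the Aim 1 penalised regression for total sleep time and delirium. Surgery type is not a listed covariate in either aim.

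Three other statements bear on the point:

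- The groups are formed by outcome; just before Section 5 the protocol states "Treatment Assignment and Randomization: Not applicable".
- On recruitment, Section 4 says "Cardiac surgical patients and orthopedic trauma patients represent the primary surgical patients that are admitted to the hospital prior to their surgical procedures".
- Section 1 says "Increasing age is a significant risk factor for the development of delirium".

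**The concern.** The delirium groups are not randomised, and on the protocol's own account delirious patients should tend to be older. They may also come more from one surgical service than the other. If clock-gene expression varies with age or service, a crude comparison mixes that variation with any link to delirium.

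This could act in either direction. A significant transcript might reflect only who becomes delirious, or a real decrease might be hidden because age or service pushes expression the other way. Correcting for multiple comparisons lowers the rejection threshold but does not remove a shift of this kind. Aim 2 is meant to inform the link between delirium and circadian disruption, so readers will want to know whether a difference survives adjustment. The plan gives them no way to tell.

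**Working it through.** **The plan's own figure.** The only sample size in the documents is in Section 7, for total sleep time: difference 60 min, SD 60 min, two-sided alpha 0.05, power 0.90, groups 1:6. Then n1 = (1 + 1/6) × (1.960 + 1.282)² × (60/60)² = 1.167 × 10.51 = 12.3, rounded up to 13, with 6 × 13 = 78 in the other group. This reproduces 13 + 78 = 91. No sample size is given for Aim 2, so 13 v 78 is used below.

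**What the documents supply and what is assumed.** They supply the test, the four genes, two-sided 0.05 and the group sizes. Bonferroni for four genes gives 0.05/4 = 0.0125; the choice of Bonferroni is an assumption, because Section 6 names no correction. The age gap between groups, the age-expression correlation, the service mix and the service shift in expression are all assumptions.

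**Size of the induced shift.** Age contributes gap × correlation. Service contributes (share in delirious − share in non-delirious) × expression difference between services, taken as 0.8 SD. The standard error of a difference in means is √(1/13 + 1/78) = 0.30 SD, the yardstick for these shifts.

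**Rejection with no delirium effect given the covariates.** Simulation with 20,000 runs per setting and normal data. The adjusted model is ordinary least squares on delirium, age and service.

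| Assumed setting | Induced shift (SD) | Rank-sum at 0.05 / 0.0125 | Adjusted at 0.05 / 0.0125 |
|---|---|---|---|
| No confounding | 0 | 4.7% / 1.0% | 4.8% / 1.2% |
| Age gap 0.5 SD, correlation 0.2 | 0.5 × 0.2 = 0.10 | 5.9% / 1.6% | 4.9% / 1.3% |
| Age gap 0.7, correlation 0.3 | 0.21 | 10.1% / 3.3% | 4.9% / 1.2% |
| Age gap 1.0, correlation 0.3 | 0.30 | 15.3% / 5.5% | 5.1% / 1.4% |
| Cardiac 60% v 50% | 0.10 × 0.8 = 0.08 | 5.8% / 1.4% | 5.1% / 1.4% |
| Cardiac 65% v 50% | 0.12 | 6.4% / 1.8% | 5.1% / 1.3% |
| Cardiac 80% v 50% | 0.24 | 10.9% / 3.5% | 4.9% / 1.2% |
| Age 0.7/0.3 and cardiac 65% v 50% | 0.21 + 0.12 = 0.33 | 16.5% / 5.9% | 4.9% / 1.3% |

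The 80% v 50% setting is strong. It implies delirium in 10.4/(10.4 + 39) = 21% of cardiac and 2.6/(2.6 + 39) = 6% of orthopedic patients.

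**Power for a true 0.8 SD decrease at 0.0125, with confounding in the opposite direction.**

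| Assumed setting | Rank-sum | Adjusted, log scale | Adjusted, ranks |
|---|---|---|---|
| No confounding | 0.50 | 0.54 | 0.50 |
| Age 0.5/0.2 | 0.38 | 0.54 | 0.51 |
| Age 0.7/0.3 | 0.25 | 0.56 | 0.52 |
| Service shift 0.8 SD, 50% v 50% | 0.42 | 0.54 | 0.50 |
| Service shift 0.8 SD, 80% v 50% | 0.19 | 0.51 | 0.49 |

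The right baseline for the last row is 0.42, not 0.50. A 0.8 SD service shift raises the variance to 1 + 0.8² × 0.25 = 1.16 even without imbalance, which by itself lowers rank-sum power. Only the fall from 0.42 to 0.19 is confounding.

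**When adjustment is not needed.** If the groups differ in age and service but neither is related to expression, power on the log scale is 0.50 against 0.50 for rank-sum (gap 0.7 SD, 65% v 50%), or 0.46 against 0.50 (gap 1.0 SD, 80% v 50%). In the second case the rank version gives 0.43.

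**Missing blood.** Section 5 warns "blood and Sedline EEG data may not be obtained on all study subjects". If 30% were missing (an assumption; 9 v 55), the adjusted model still rejects 4.9% at nominal 5% under the null.

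**The case against.** The strongest reply is that the plan tests what it says it tests. Hypothesis 2.1 claims an association, and a rank-sum test is valid for that. If age creates a real crude difference in expression, rejecting is not a false positive for that hypothesis. It misleads only when read as independent of age or service, which the plan does not claim. This stands.

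Half of the confounding path is also missing. The documents tie age to delirium, but they tie neither age nor service to expression and give no delirium rate by service. Entry at 60 or over narrows the age range. In the mildest settings above the distortion is negligible (about 6% at nominal 5%). This stands too.

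The stakes are limited: Section 7 makes sleep duration the primary objective, and the sentence after the Aim 2 test opens by referring to other exploratory analysis.

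A reader might infer that the Aim 2 analysis is invalid, or that its false-positive rate is 17%. The documents support neither. The 17% is the top of an assumed range, for a null that is conditional on the covariates. Nor would adjustment put the two aims on the same footing, since Aim 1 lists seven covariates and omits surgery type.

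The objection that 13 events cannot carry covariates does not apply. Expression is the outcome in the adjusted model, so up to about 91 observations support three predictors.

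Which blood draw tests the hypothesis, how many tests are corrected for, and the clock time of each draw are separate gaps in detail. This point does not depend on them.

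**Conclusion.** This is a cheap improvement, not an error. The planned tests answer the crude question in Hypothesis 2.1. They cannot show whether a difference is independent of age or surgical service, and nothing else in the plan can either.

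How much this matters cannot be found from the documents. With 13 v 78, normal data and the assumed confounding strengths, rank-sum rejection runs from about 5% to 17% at nominal 5% (1% to 6% at 0.0125), while the adjusted model stays at about 5% (about 1.2%). Masking of a true 0.8 SD decrease ranges from modest (0.50 to 0.38) to serious (0.50 to 0.25 for age; about 0.42 to 0.19 for service). Adjusted power holds at about 0.51 to 0.56 on the log scale, or 0.49 to 0.52 on ranks. Those ranges illustrate what is possible; they do not estimate what will happen in this cohort.

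**What to change.** In Section 6, keep the rank-sum test for the crude association. For each transcript add one pre-specified linear regression of log2 expression on delirium, age and surgery type (cardiac or orthopedic), under the same multiplicity correction. Name the log2 scale as the single choice, so that the transformation is not picked after the data are seen. State that any claim beyond a crude association rests on the adjusted estimate and its confidence interval.

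The cost is a few lines of plan wording and a little more analysis. No new samples are needed, and age and surgery type are already known for every patient. There are three downsides:

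- Adjustment can lose some power when age and service differ between groups but are unrelated to expression (0.50 to about 0.46 in the worst case tried).
- There will be two results per transcript, which may disagree; the sentence saying which supports which claim deals with this.
- Unmeasured confounding remains, so the adjusted estimate is still observational.

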#### 7. POWER ANALYSIS

The primary objective of this trial is to detect a difference in the duration of sleep between delirious and nondelirious patients. Assuming a delirium event rate of 15%, a type I error of 0.05, power of 0.90 and a SD of 60 minutes, n = 13 patients with delirium and 78 patients without delirium will enable us to detect an absolute total sleep time difference of 60 minutes between both groups (i.e., 360 minutes versus 300 minutes). Therefore, anticipating a dropout rate of approximately 10%, we aim to recruit 100 subjects.

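### The exploratory EEG spectral rule in section 6 is not calibrated across the spectrum, so its chance of declaring at least one false band is unknown and can exceed 0.05

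*Combined protocol and SAP*

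**What the plan says.** Section 6 (Data Analysis Plan) opens with a general level: "Hypothesis tests will be performed using a two-sided significance level (type I error) of" 0.05. The EEG work comes later in the section and is labelled exploratory: "In other exploratory analysis, we will assess differences in the EEG (PSG and intraoperative) dynamics of delirious and non-delirious patients". At each frequency, "we will compute the 99% confidence interval of the median difference between groups by using an empirical bootstrap approach". The decision rule follows: "The null hypothesis will be rejected only if the confidence interval of the median difference at each frequency exceeds the significance threshold", and this must hold over a contiguous range of at least 2W.

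The section does not define W, the significance threshold, the frequency range, which bootstrap interval is meant, what is resampled, or how the PSG and intraoperative results are to be taken together. Multiplicity is addressed by name only for Aim 2, where "Wilcoxon rank-sum tests with corrections for multiple comparisons will be used".

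Section 7 (Power Analysis) plans for "n = 13 patients with delirium and 78 patients without delirium". Section 5 (Study Design) allows that PSG and intraoperative EEG recordings may be missing for some subjects.

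**The concern.** A 99% interval at one frequency limits the error at that frequency. The rule scans every frequency and rejects wherever it finds a long enough run, so the relevant error is the chance of finding any such run when the groups do not differ. The run requirement reduces that chance, but by how much depends on how far patients' spectra are correlated across frequency. If a patient who is high at one frequency tends to be high several hertz away, chance excursions come in wide blocks, and a run of 2W is easy to obtain.

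The interval raises a second question. A percentile bootstrap interval for a median behaves much like an interval between order statistics and roughly keeps its level. A basic interval reflects those limits about the estimate and loses that property, which matters with a group of about 13. The plan's term does not settle which is meant.

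The practical risk is that a chance band is reported as an EEG signature of delirium. Section 1 (Background and Significance) presents sleep EEG features as a possible way to identify patients at risk, so such a finding could be taken further.

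**Working it through.** **Group sizes.** These come from section 7, and the plan's figure reproduces. With SD 60, difference 60, two-sided 0.05, power 0.90 and a 1:6 ratio, the smaller group needs (1 + 1/6) × (1.960 + 1.282)² × (60/60)² = 12.3, so 13, and 6 × 13 = 78. Power at 13 v 78 is 0.916 (normal approximation). The calculation is for total sleep time; only the group sizes are used below.

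**Scale without a run rule.** For k independent tests at 0.01 the chance of any rejection is 1 − 0.99^k: 0.059 at k = 6 and 0.182 at k = 20.

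**Simulation of the rule under no difference.** Assumptions not in the documents: Gaussian log-power; bootstrap resampling of patients; threshold of zero; the frequency grid; 2W; and a correlation length L for between-patient spectra. With q the bootstrap quantiles and d the observed median difference, the percentile interval is (q0.005, q0.995) and the basic interval is (2d − q0.995, 2d − q0.005). Rejection means a same-sign run of at least 2W anywhere.

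*Pointwise error, nominal 0.01, 13 v 78.* Separate runs gave about 0.07, 0.079 and 0.087 for the basic interval, and about 0.01 for the percentile interval.

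*Chance of at least one false band*, 0.5-40 Hz in 0.25 Hz bins, 600 null data sets per row, bin centres required to span 2W:

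| 2W (Hz) | L (Hz) | Percentile | Basic |
|---|---|---|---|
| 1 | 0.5 | 0.007 | 0.042 |
| 1 | 1 | 0.050 | 0.218 |
| 1 | 2 | 0.128 | 0.440 |
| 1 | 4 | 0.115 | 0.582 |
| 1 | 8 | 0.093 | 0.550 |
| 1 | 20 | 0.045 | 0.377 |
| 2 | 1 | 0.000 | 0.012 |
| 2 | 2 | 0.035 | 0.103 |
| 2 | 4 | 0.053 | 0.260 |
| 2 | 8 | 0.070 | 0.343 |
| 2 | 20 | 0.022 | 0.310 |
| 4 | 4 | 0.007 | 0.053 |
| 4 | 8 | 0.027 | 0.123 |

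The Monte Carlo standard error is about 0.014 at 0.13.

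*Correlation confined to 2W* (triangular kernel, 2W = 1 or 2 Hz): 0 with the percentile interval and 0 to 0.008 with the basic interval.

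*Coarser grid* (0.5-30 Hz in 0.5 Hz bins, 2W of 1-2 Hz, L of 1-8 Hz), across ways of counting a run: roughly 0 to 0.18 percentile and 0.02 to 0.68 basic. Counting matters. At 2W = 1 Hz and L = 1 Hz, treating two adjacent bins as a 1 Hz run gave 0.15 percentile and 0.60 basic; requiring bin centres to span 1 Hz gave 0.05 and 0.21.

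**Two EEG sources.** If PSG and intraoperative results were independent, a rate of 0.05 each becomes 1 − 0.95² = 0.10, and 0.13 each becomes 1 − 0.87² = 0.24.

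**Check on the alternative.** A patient-level permutation test on the largest cluster, run under no difference in settings of this kind, gave spectrum-wide error of 0.02-0.04.

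**The case against.** The case for leaving the rule alone has real weight. The analysis is labelled exploratory, is not one of the Aim hypotheses in section 2, and is not the primary objective in section 7. The plan already tightens the pointwise level to 99% and adds a contiguity requirement, and both are genuine protections against chance bands. Many percentile-interval settings in the table are at or below 0.05. When correlation is confined to 2W the rule almost never rejects falsely. It is therefore not enough to argue that neighbouring frequencies within 2W are correlated: the inflation needs between-patient correlation that reaches further, and that is an assumption.

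A reader might infer that the rule produces false bands far more often than the plan's stated 0.05. The documents do not support that. The 0.05 is a general test level and is not given as a family-wise level for the spectra. The largest rates need the basic interval, which the plan's wording permits but does not specify. W is undefined, so treating it as the bandwidth of the spectral estimator is only a reading. The 13 v 78 split was planned for total sleep time, so the EEG group sizes are also assumed.

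What remains is that the plan uses null-rejection language for a rule whose error rate it neither states nor calibrates. The choices that move that rate from near zero to above one half could be made after the spectra are seen.

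**Conclusion.** The concern holds as a lack of calibration; a known inflation is not shown. Under the coarser-grid assumptions the chance of at least one false band in one set of spectra is roughly 0 to 0.18 with a percentile interval and 0.02 to 0.68 with a basic interval. The firmest single result is that, at 13 v 78, the basic interval's nominal 1% pointwise error is about 7-9%. Fewer than 13 delirious patients may have spectra. All these figures rest on Gaussian log-power, patient-level resampling, a zero threshold and assumed values for W, the grid and the correlation length. Because the analysis is exploratory, the consequence is limited to how EEG findings are labelled. The change is worth making because it is cheap; the study's primary conclusion is not affected.

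**What to change.** Replace the rejection sentence in section 6 with a permutation test at patient level:

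- Pre-state the frequency range for each EEG source.
- Permute the delirium labels across patients and recompute the median difference at each frequency.
- Form clusters of contiguous, same-sign frequencies beyond a pre-stated pointwise threshold, for example the two-sided 1% permutation cut-off, and state how cluster size is measured (width in Hz, say).
- Compare the largest observed cluster, of either sign, with the permutation distribution of the maximum, at two-sided 0.05 overall: 0.025 for PSG and 0.025 for intraoperative EEG. Otherwise, state that each source is tested separately as exploratory.
- Show percentile bootstrap intervals, resampling patients, as display only.

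The permutation null is that spectra are exchangeable between the groups, so a rejection could partly reflect a difference in spread; the displayed intervals help in reading it. If the investigators prefer to keep the present rule, the least that would do is to define W, the threshold, the range, the interval type and the resampling unit, and to report the spectra as descriptive.

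The cost is a short SAP revision and a short program, with no new data. The downside is that fewer bands may be called significant.

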#### **Pooled Analysis Summary**

A total of 1,199 patients and 244 cases of delirium were analyzed. We found that the pooled odds ratio for the association between sleep disturbance and POD was 5.24 (95% CI: 3.61 to 7.60, p <0.001; l=0.0%, p=0.76). The pooled odds ratio for the association between pre-delirium sleep disturbance and POD of 5.24 (95% CI: 3.61 to 7.60, p <0.001; I=0.0%, p=0.76; Fig 2b) was statistically significant. The odds ratio associated with obstructive sleep apnea and unspecified types of sleep disorder were 4.75 (95% CI: 2.65 to 8.54, p <0.001; I=0.0%, p=0.85), and 5.60 (95% CI: 3.46 to 9.07, p <0.001; l=0.0%, p=0.41), respectively. We conducted a sensitivity analysis using risk ratios obtained from the prospective studies,  and found that the pooled risk ratio for the association between sleep disturbance and POD of 2.90 (95% CI: 2.28 to 3.69, p <0.001; l=0.0%, p=0.89; Fig 5) was significant.

Figure 1. Pooled analysis of studies with crude odds ratio

Evans et al., in a pilot prospective study that used EEG recordings to objectively study predictors of POD, found that diminished sleep time and increased sleep latency on POD 1 is associated with increased incidence and severity of delirium. Sleep disturbance is a hallmark feature of the postoperative period, and results from this study do not resolve whether pre-existing sleep disturbance is associated with an increased incidence of POD. Other studies that have evaluated the association between sleep disorder and delirium have utilized measures such as wrist actigraphy or the Pittsburgh Sleep Quality Index (PSQI) to evaluate sleep disturbance. Unfortunately, the use of actigraphy or the PSQI in isolation do not provide accurate details on sleep quality or microstructure dynamics of sleep such as slow-delta oscillations, sleep spindles, K-complexes or REM alpha oscillations. These dynamics, which may aid the pre-emptive identification of patients that are prone to developing POD, can be obtained using a portable sleep polysomnography (PSG) device.

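### The exploratory PSG spectra and sleep-microstructure contrasts have no age adjustment, and the plan does not say whether the spectra are computed within sleep stages

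*Combined protocol and SAP*

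**What the plan says.** Section 6 (Data Analysis Plan) introduces the EEG work as exploratory: "we will assess differences in the EEG (PSG and intraoperative) dynamics of delirious and non-delirious patients". For the spectra it specifies a two-group bootstrap 99% confidence interval of the median difference at each frequency. The null is rejected only where the criterion is met over a contiguous range of at least 2W. For spindle power, rate and peak frequency and for slow-delta/spindle coupling it says "We will also characterize differences in sleep microstructure dynamics" between groups with in-house algorithms. It names no test, model or covariate for these.

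Age, gender, baseline cognitive score and the other patient characteristics are assigned to the Aim 1 regression only.

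Three other places bear on this:

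- Section 1: "Increasing age is a significant risk factor for the development of delirium". Section 3 admits patients from age 60 with no upper limit.
- Pooled Analysis Summary, on why PSG is used: "These dynamics, which may aid the pre-emptive identification of patients that are prone to developing POD".
- Section 2, Hypothesis 1.1, expects cases to sleep less before surgery. Section 7 puts the figures at 300 versus 360 minutes.

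Section 5 places the PSG at about 7 pm, removes it at about 6 am, and lists a minimum electrode set for sleep staging. Section 6 does not say whether the spectra are computed within scored stages, on sleep epochs only, or over the whole record.

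**The concern.** By the protocol's own statement, delirious patients will tend to be older. If spectral power, spindle measures or coupling also change with age, a crude contrast mixes the age difference with any difference tied to delirium. The protocol motivates PSG by its possible use in picking out patients at risk. Age is already known for every patient, so a crude difference cannot show that these measures add anything to it. The protocol adjusts for age when it relates total sleep time to delirium, but not when it compares other measures from the same recording.

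The second issue is conditional and concerns the spectra only. If a spectrum were averaged over the whole record, cases would contribute a larger share of wake simply because they sleep less. The groups would then differ even if the EEG within every stage were identical, and Hypothesis 1.1 would reappear as a spectral finding.

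**Working it through.** **The plan's own figure.** Section 7 uses "a type I error of 0.05, power of 0.90 and a SD of 60 minutes" and arrives at "n = 13 patients with delirium and 78 patients without delirium". For a 60-minute difference (1 SD), a 1:6 ratio and two-sided 5%, the smaller group is (1.960 + 1.282)² × (1 + 1/6) = 10.51 × 1.167 = 12.3, rounded up to 13, with 6 × 13 = 78 in the other. The noncentral t gives power 0.91. The group sizes reproduce. No sample size is stated for the EEG contrasts, so 13 versus 78 is used below. Section 5 warns that some subjects may have no PSG, so the real numbers may be smaller.

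**Age. Assumptions, not in the documents:** cases older by D = 0.4, 0.6 or 0.8 SD of age; correlation of the measure with age r = 0.3, 0.4 or 0.5; no effect of delirium once age is known.

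Spurious standardised difference = D × r. Its standard error is √(1/13 + 1/78) = 0.300. Noncentrality is the ratio of the two, with 89 degrees of freedom.

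| D | r | Shift (SD) | Noncentrality | Rejects at 1% | Rejects at 5% |
|---|---|---|---|---|---|
| 0.4 | 0.3 | 0.12 | 0.40 | 1.6% | 7% |
| 0.6 | 0.4 | 0.24 | 0.80 | 3.7% | 12% |
| 0.8 | 0.5 | 0.40 | 1.34 | 10.3% | 26% |

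The 1% column matches the 99% interval set for each spectral frequency, before the contiguity rule. The 5% column applies to microstructure only if the general level in Section 6 is used with a comparable test.

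**Check on the bootstrap itself.** The unadjusted bootstrap 99% interval for the median difference was simulated with 13 versus 78 patients (1,500 data sets, 600 resamples each). It was set beside a linear model containing age, tested at 1%.

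| Age gap (SD) | Correlation | Crude interval excludes zero | Linear model with age rejects |
|---|---|---|---|
| 0 | 0.4 | 1.3% | 1.1% |
| 0.5 | 0.3 | 1.5% | 1.3% |
| 0.5 | 0.5 | 3.5% | 0.8% |
| 1.0 | 0.3 | 4.2% | 0.9% |
| 1.0 | 0.5 | 12.1% | 1.3% |

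The bias is negligible for a small gap or weak correlation and material when both are large. Adjustment returns the error to about 1%.

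**Stage mix, only if spectra are taken over the whole record.** From 7 pm to 6 am is 660 minutes. The sleep share s is 300/660 = 45.5% in cases and 360/660 = 54.5% in non-cases. If power in a band is k times higher asleep than awake (k assumed), mean power is proportional to s × k + (1 − s).

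| k | Cases | Non-cases | Ratio | 10 × log10(ratio) |
|---|---|---|---|---|
| 3 | 1.909 | 2.091 | 0.913 | −0.40 dB |
| 5 | 2.818 | 3.182 | 0.886 | −0.53 dB |
| 10 | 5.091 | 5.909 | 0.862 | −0.65 dB |

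**The case against.** The best defence is that these analyses are exploratory, lie outside both aims and their hypotheses, and leave the primary result alone. A crude contrast is an ordinary first description, and adjustment could be added at reporting. That stands and limits the weight of the point. It does not remove the confounding, and these are the measures the protocol puts forward as possibly useful for identifying at-risk patients.

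Four stronger readings are tempting, and the documents do not support them:

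- **That the plan pools sleep stages.** It does not say so. Staging electrodes are placed, and total sleep time itself requires sleep to be scored. The plan is silent, so the stage-mix deficit is a conditional risk.
- **That the stage mix also distorts the microstructure results.** Spindles and slow-delta/spindle coupling are features of sleep, and the protocol calls them sleep microstructure. The stage argument is therefore kept to the spectra.
- **That the spectral tests run at 12% error.** That figure belongs to a 5% test. Under the stated 99% interval the central figure is 3.7%. The contiguity rule makes isolated chance findings less likely, although a systematic age shift across a band could still pass it.
- **That the plan claims a marker of delirium independent of age.** It says only that the dynamics may help identification.

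It is also fair to object that the documents give no figure for age and sleep EEG and no expected age gap, so the age result rests on assumed ranges. The decibel figures likewise cannot be turned into an error rate without a between-patient SD, which is not given.

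**Conclusion.** The point holds as a cheap improvement. Section 6 specifies an unadjusted two-group contrast for the spectra and names no covariate for microstructure, while Section 1 ties delirium to age.

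The size of the age effect depends on an assumed age gap of 0.4 to 0.8 SD, an assumed correlation of 0.3 to 0.5, and PSG in all 13 and 78 patients. On that basis, error per spectral frequency is about 1.6% to 10% (central 3.7%) against 1%, before the contiguity rule. It would be 7% to 26% (central 12%) against 5% for a microstructure measure if a 5% test were used.

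On stage, the finding is an unstated choice. Its possible consequence is a deficit of about 0.4 to 0.65 dB in cases if spectra cover the whole record and power is 3 to 10 times higher asleep. Interpretation of the exploratory PSG findings is affected; the primary comparison of sleep time is not.

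**What to change.** Add to Section 6:

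1. For each PSG spectral and microstructure measure, report an age-adjusted group difference beside the crude one, from a linear or median regression of the measure on POD and age. Keep the bootstrap interval for the spectra.
2. State that PSG spectra are computed within scored sleep stages.
3. Base any statement about identifying at-risk patients on the adjusted result.

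The sleep measure is the dependent variable and only age is added, so the small number of cases is not an obstacle. The argument here is about age and gives no ground for requiring further covariates.

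The cost is a little more analysis on data already collected, and the loss of patients with too little of a given stage. Precision need not suffer. At the central assumptions, adding age to a linear model multiplies the standard error by about 0.94: √(1 + 0.6²/(0.0897 × 89)) = 1.02 for collinearity, where 0.0897 = 1/13 + 1/78, times √(1 − 0.4²) = 0.92 for residual SD. With a weaker correlation the intervals could be slightly wider.
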